3.9 MANAGEMENT OF SPECIFIC AEs

Recommendations for modifications of the dosing regimens based on the drug and the type and severity of AEs or laboratory abnormalities are provided in Table 3-2. The recommendations provided in Table 3-2 comprise only guidelines; variations from these recommendations may be warranted based on an investigator's individual judgment in considering potential risks, benefits, and therapeutic alternatives available to each subject. Whenever possible, any interventions for potential treatment-related AEs should be discussed between the investigator and the medical monitor before implementation.

Please refer to Section 4.1.9 for dose modifications based on QTc AEs.

Table 3-2. Recommendations for Acalabrutinib and ACP-319 Dose Modifications Based on Type and Severity of Treatment-Related Adverse Events or Laboratory Abnormalities

| Recommendation | | | | | |
|----------------------------------------------------------------------------------|--------------------------------------------------------------------------------------------------------------------------------------------------------------------------------------------------------------------------------------------------------------------|--------------------------------------------------------------------------------------------------------------------------------------------------------------------------------------------------|--|--|--|
| NCI CTCAE Grade | Acalabrutinib | ACP-319 | | | |
| Gastrointestinal Inflammation/Diarrhea | | | | | |
| Grade 1 Mild diarrhea: Increase of < 4 stools per day over baseline | Provide antidiarrheal (e.g., loperamide) and maintain current acalabrutinib dose level and schedule. Provide antidiarrheal (e.g., loperamide). Withhold acalabrutinib until Grade <1. | Provide antidiarrheal (e.g., loperamide) and maintain current ACP-319 dose level and schedule. Provide antidiarrheal (e.g., loperamide) and maintain current ACP-319 dose level and | | | |
| Grade 2 Moderate diarrhea: Increase of 4–6 stools per day over baseline | Resume acalabrutinib at current dose level. If rechallenge results in recurrence, may resume at initial or lower dose level at investigator discretion (if applicable). Consider addition of anti-inflammatory (e.g., sulfasalazine, budesonide). | schedule. Monitor at least weekly until resolved. Consider addition of anti-inflammatory (e.g., sulfasalazine, budesonide). | | | |

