| Grade 3 (ALT/AST >5-20 x ULN) (Bilirubin >3-10 x ULN) | Withhold or continue acalabrutinib (at investigator discretion, after discussion with the medical monitor). Monitor ALT, AST, ALP, and bilirubin at least 1x per week. After 7 days if hepatic enzymes appear to be improving and acalabrutinib was withheld, restart acalabrutinib at current dose level. | Withhold ACP-319. Monitor ALT, AST, ALP, and bilirubin at least 1x per week until all abnormalities have returned to Grade ≤1. Recommend treating with high dose oral or IV corticosteroids (at a dosage of 40 mg prednisone or equivalent QD) for at least 48 hours; when all abnormalities have returned to Grade ≤1, recommend tapering steroids over no <4 weeks. Once abnormalities have returned to Grade ≤1, ACP-319 may resume at initial or lower dose level (if applicable). |
| Grade 4 | See recommendations for | Discontinue ACP-319 |
| (ALT/AST >20 x ULN) | Grades 2 or 3 | permanently. |
| (Bilirubin >10 x ULN) | | |
| | | diffuse interstitial pattern or |
| ground-glass opa | cities on chest CT and no d | |
| Grade 1 | Maintain current dose level and schedule. Consider pneumocystis prophylaxis. | Discontinue ACP-319 permanently. |
| Grade 2 | Withhold acalabrutinib until Grade ≤1, consider systemic corticosteroids and pneumocystis treatment. May resume at initial or lower dose level (if applicable) at investigator discretion. | Discontinue ACP-319 permanently. |
| Grade ≥≥3 | Withhold acalabrutinib until Grade ≤1, consider systemic corticosteroids and consider pneumocystis treatment. May resume at lower dose level (if applicable) or discontinue acalabrutinib at investigator discretion. | Discontinue ACP-319 permanently. |

Table 3-2. Recommendations for Acalabrutinib and ACP-319 Dose Modifications Based on Type and Severity of Treatment-Related Adverse Events or Laboratory Abnormalities

| Recommendation | | | | | |
|-----------------|-----------------------------------------------------------------------------------------------------------------------------------------------------------------------------------------------------------------------------------------------------------------------------------------|-------------------------------------------------------------------------------------------------------------------------------------------------------------|--|--|--|
| NCI CTCAE Grade | Acalabrutinib | ACP-319 | | | |
| | Neutropenia | | | | |

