3.9.2 Elevated Liver Function Tests and Immune-Mediated Hepatitis

In subjects with lymphoid malignancies, reversible serum ALT/AST elevations have been observed (Furman et al. 2010, Kahl et al. 2010) with idelalisib. In these subjects, onset has typically occurred within 2 to 16 weeks of starting the PI3Kδ inhibitor therapy.

Among subjects receiving ACP-319 with Grade 1 to 2 ALT/AST abnormalities, continued dosing has been possible; transaminase values commonly resolve despite continued PI3K δ inhibitor treatment. For those with Grade 3 to 4 ALT/AST elevations, drug interruption has resulted in resolution over 2 to 6 weeks. Successful rechallenge at lower dose levels of PI3K δ inhibitor has been achieved in most subjects. Thus, in subjects with uncomplicated hepatic laboratory abnormalities, the instructions in Table 3-2 should be followed in an attempt to maximize the potential that subjects who appear to be benefiting can continue with study drug treatment.

In selected subjects who experience more complicated hepatic AEs, further workup may be warranted, particularly in subjects who first experience a serum ALT/AST elevation ≥12 weeks from the start of study drug therapy, who have an elevation in serum bilirubin concentration or change in coagulation parameters, or who have other characteristics that suggest a change in liver function. Further workup may include the following: obtaining a history of recent symptoms/illnesses and of relevant past history (e.g., history of hepatitis or of hepatitis A or hepatitis B vaccination); obtaining information regarding concomitant drug use (prescription and nonprescription medications, dietary supplements, alcohol, illicit drugs, special diets); questioning the subject regarding potential exposure to environmental toxins; ruling out viral hepatitis A, B, C, D (if hepatitis B is positive), and E, Epstein-Barr virus, CMV, autoimmune hepatitis, alcoholic hepatitis, nonalcoholic steatohepatitis, hypoxic/ischemic hepatopathy, and biliary tract disease; obtaining additional tests to evaluate liver function (e.g., prothrombin time [PT], activated partial thromboplastin time, international normalized ratio [INR], albumin); and

Protocol: ACE-LY-001

considering gastroenterology or hepatology consultation (Food and Drug Administration. Guidance for industry. Drug-induced liver injury: premarketing clinical evaluation. 2009 Jul). Hepatic AEs that require additional workup should be discussed with the medical monitor.

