3.10.2 Prohibited or Restricted Concomitant Therapy

Any chemotherapy, immunotherapy, kinase inhibitors, bone marrow transplant, experimental therapy, or radiotherapy for treating lymphoid cancer are prohibited.

Localized, short courses of radiotherapy are allowed for the treatment of lesions unrelated to the disease under study, if approved by the medical monitor.

Warfarin or equivalent vitamin K antagonists (e.g., phenprocoumon) are prohibited.

At study entry, subjects may be using topical or inhaled corticosteroids or low-dose steroids (≤10 mg of prednisone or equivalent per day) as therapy for comorbid conditions but use of corticosteroids as therapy of the lymphoid cancer is not permitted. During study participation, subjects may also receive systemic or enteric corticosteroids at any required dosage as needed for treatment-emergent comorbid conditions such as treatment-emergent colitis or pneumonitis.

Use of omeprazole, esomeprazole, lansoprazole, or any other proton-pump inhibitors is prohibited at study entry. The decision to treat with proton-pump inhibitors during the study is at the investigator's discretion, with an understanding of the potential benefit to the subject's GI condition and a potential risk of decreased exposure to acalabrutinib.

Subjects should avoid the use of calcium carbonate-containing drugs or supplements for a period of at least 2 hours before and at least 2 hours after taking acalabrutinib. Although the effect of H2-receptor antagonists (such as famotidine or ranitidine) on acalabrutinib absorption has not been evaluated, if treatment with an H2-receptor antagonist is required, the H2-receptor antagonist should be taken approximately 2 hours after an acalabrutinib dose.

The concomitant use of strong inhibitors/inducers of CYP3A (see Appendix 3) should be avoided when possible. If a subject requires short-term treatment with a strong CYP3A inhibitor (such as anti-infectives for up to 7 days), interrupt acalabrutinib treatment. Conversely concomitant administration of a strong inducer of CYP3A has the potential to decrease exposure of ACP-319 or acalabrutinib and could reduce the efficacy of the study drugs. For additional information on drugs with potential drug-drug interactions, refer to Section 3.11.3.

Use of medications known to prolong QTc interval or that may be associated with Torsades de pointes (see Appendix 2) are prohibited within 7 days of starting study drug and during Day 1 to 28 inclusive of Cycle 1.

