4.1.22 Tumor Assessments

DLBCL (non-GCB and GCB), MCL, FL, CLL/SLL, RS, and WM:

A pretreatment CT scan with contrast (unless contraindicated) is required of the chest, abdomen, and pelvis and any other disease sites (e.g., neck) within 30 days before the first dose of study drug. A pretreatment positron-emission topography (PET)/CT scan is optional; however, if a recent PET/CT scan (within 90 days of the first dose) is available, the information will be recorded. Information on extranodal involvement will also be recorded.

For subjects with baseline (screening) extramedullary disease, on-treatment CT scans with contrast (unless contraindicated) of the chest, abdomen, and pelvis and any other disease sites (e.g., neck) will be done for tumor assessments at the end of Cycle 2 (±7 days), Cycle 4 (±7 days), and Cycle 6 (±7 days); every 3 cycles (12 weeks, ±7 days) through Cycle 18, and then every 6 cycles thereafter, or more frequently at investigator discretion. A CT scan is also done at the TT visit, if not done at the time of disease progression. Depending on the tumor type (eg MM, B-ALL, or WM in the absence of baseline extramedullary disease), on-study tumor assessments may be done by laboratory studies. Bone marrow and PET/CT are required for confirmation of CR per clinical guidelines (see Section 4.2).

Subjects should have radiographic tumor measurements done at the participating study center or an acceptable alternate imaging facility using an identical imaging protocol and similar equipment. The same imaging equipment should be used for all scans whenever possible. The same radiologist should be assigned to read all the scans for a given subject throughout the study.

Protocol: ACE-LY-001

In the event disease progression is suspected due to physical examination or laboratory test, a CT and/or PET/CT scan must be performed to confirm disease progression.

There must be radiographically measurable disease at screening (≥1 lymph node >2.0 cm in the longest diameter). If the sole lesion lies within the field of prior radiotherapy, there must be evidence of disease progression in that lesion.

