4.2 INVESTIGATOR'S ASSESSMENT OF RESPONSE TO TREATMENT

The investigator must rate the response of the subject's non-Hodgkin lymphoma (NHL) or RS, CLL/SLL, WM, B-ALL, or MM as outlined below:

NHL or RS refer to Table 4-4

CLL/SLL refer to Table 4-5

WM refer to Table 4-6

B-ALL refer to Table 4-7

MM refer to Table 4-8

Response assessments should not be performed while subjects are receiving systemic or enteric corticosteroids for treatment-emergent comorbid conditions.

Note: Transient worsening of disease during temporary interruption of study therapy (e.g., for drug-related toxicity, surgery, or intercurrent illness) may not indicate disease progression. In such circumstances, and if medically appropriate, subjects may resume therapy and relevant clinical, laboratory, and/or radiographic

Protocol: ACE-LY-001

assessments should be done to document whether tumor control can be maintained or whether actual disease progression has occurred.

Protocol: ACE-LY-001

Table 4-4. Response Assessment Criteria for NHL

| Response and Site | PET-CT-Based Response | CT-Based Response |
|---------------------------------------|---------------------------------------------------------------------------------------------------------------------------------------------------------------------------------------------------------------------------------------------------------------------------------------------------------------------------------------------------------------------------------------------------------------------------------------------------------------------------|-----------------------------------------------------------------------------------------------------------------------------|
| Complete | Complete metabolic response | Complete radiologic response (all of the following) |
| Lymph nodes and extra lymphatic sites | Score 1, 2, or 3 ^a with or without a residual mass on 5PS ^b | Target nodes/nodal masses must regress to ≤1.5 cm in LDi |
| | It is recognized that in Waldeyer's ring or extranodal sites with high physiologic uptake or with activation within spleen or marrow (e.g., with chemotherapy or myeloid colony-stimulating factors), uptake may be greater than normal mediastinum and/or liver. In this circumstance, complete metabolic response may be inferred if uptake at sites of initial involvement is no greater than surrounding normal tissue even if the tissue has high physiologic uptake | No extralymphatic sites of disease |

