5.4.4 Analysis of Efficacy Parameters

Response Rate

The primary efficacy endpoint is the ORR as assessed by investigators. ORR is defined as the proportion of subjects who achieve a response (see Table 4-4, Table 4-5, Table 4-6, Table 4-7, and Table 4-8). ORR will be calculated and the corresponding 2-sided 95% CI will be derived.

In addition, for subjects with CLL/SLL, response will be assessed according to Table 4-5, which reflects modified International Working Group response criteria (Hallek et al. 2008)

Protocol: ACE-LY-001

as recently updated (Cheson et al. 2012) to include partial remission (response) with treatment-induced lymphocytosis (PRL). For purposes of this analysis, lymphocytosis at a given timepoint will be defined as ALC, which is above normal limits and is not ≥50% decreased from baseline.

Duration of Response

The duration of response defined as the interval from the first documentation of response to the earlier of the first documentation of definitive disease progression or death from any cause. Kaplan-Meier methods will be used to estimate event-free curves and corresponding quantiles (including the median). Data from surviving, non-progressing subjects will be censored at the earliest of the time of initiation of anticancer treatment other than the study treatment or the last time that lack of disease progression was objectively documented. Data from subjects who have disease progression or die after ≥2 consecutive missing tumor assessments will be censored at the last time before the missing assessments that lack of disease progression was objectively documented.

Progression-Free Survival

Progression-free survival is defined as the interval from the start of acalabrutinib and ACP-319 therapy to the earlier of the first documentation of objective disease progression or death from any cause. Kaplan-Meier methods will be used to estimate the event-free curves and corresponding quantiles (including the median). Data from surviving, non-progressing subjects will be censored at the earliest of the time of initiation of anticancer treatment other than the study treatment or the last time that lack of disease progression was objectively documented. Data from subjects who have disease progression or die after ≥2 consecutive missing tumor assessments will be censored at the last time prior to the missing assessments that lack of disease progression was objectively documented.

Time-to-Next Treatment

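### Section 4.2 bars response assessments during steroid treatment of toxicity, contradicting the scan rules in Section 4.1.22 and delaying documented progression in subjects with toxicity

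*Protocol*

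**What the plan says.** Section 4.2 assigns a response table to each disease and then states: "Response assessments should not be performed while subjects are receiving systemic or enteric corticosteroids for treatment-emergent comorbid conditions." Those tables define progression as well as response, and no exception is made for progression.

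Section 3.10.2 shows which conditions are meant. During the study "subjects may also receive systemic or enteric corticosteroids at any required dosage as needed for treatment-emergent comorbid conditions such as treatment-emergent colitis or pneumonitis". In Table 3-2 (Section 3.9), the ACP-319 column for Grade 3 hepatic events recommends steroids for at least 48 hours, and "when all abnormalities have returned to Grade ≤1, recommend tapering steroids over no <4 weeks". Section 3.9.2 adds: "For those with Grade 3 to 4 ALT/AST elevations, drug interruption has resulted in resolution over 2 to 6 weeks." The table also suggests considering budesonide from Grade 2 diarrhea, and systemic steroids for pneumonitis and rash. It gives no durations for these.

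Three other sections bear on the same assessments:

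- **Section 4.1.22** schedules CT at the ends of Cycles 2, 4 and 6, every 3 cycles to Cycle 18, and every 6 cycles after that. On-treatment scans to Cycle 18 have ±7-day windows. No steroid exception is stated. On suspected progression "a CT and/or PET/CT scan must be performed to confirm disease progression".
- **Section 4.5** has missed evaluations made up near their planned date. One may be dropped if rescheduling brings it too close to the next.
- **Section 5.4.4** dates progression at its first documentation and counts death from any cause. It adds: "Data from subjects who have disease progression or die after ≥2 consecutive missing tumor assessments will be censored at the last time" before the gap at which absence of progression was documented.

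**The concern.** The bar is triggered by treatment of a treatment-emergent condition. A subject on low-dose steroids for a pre-existing condition is not covered. Assessment therefore becomes sparser specifically in subjects with toxicity, who may also have had study drug interrupted. Because progression is dated when it is first documented, a withheld assessment moves the event later. That missingness is informative, and it pushes PFS and duration of response upward.

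There is also a plain conflict for sites. If progression is suspected during a steroid course, Section 4.1.22 requires a scan while Section 4.2 says response should not be assessed. The note that follows in Section 4.2 itself asks for assessments after an interruption for toxicity, to establish whether progression has occurred.

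**Working it through.** The protocol gives no figure for this effect, so there is none to reproduce. The check is one of timing.

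**Inputs.**
- A cycle is 28 days (Section 3.0), so scan intervals *I* are 8 weeks to Cycle 6, 12 weeks to Cycle 18, then 24 weeks (Section 4.1.22).
- Course length *L*: 2-6 weeks to resolution (Section 3.9.2) plus a taper of at least 4 weeks (Table 3-2) gives about 6-10 weeks. This is an assumption. It takes steroids as continuing until Grade ≤1, whereas the table specifies only at least 48 hours before the taper.
- The course starts at a uniformly random time between scheduled scans.

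**At least one assessment blocked.** On nominal dates, P = min(1, *L*/*I*). If a visit is blocked only when its whole two-week window lies inside the course, P = min(1, (*L* − 2)/*I*). The window version is in brackets. For the 24-week interval the same ±7 days is assumed.

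| Interval | *L* = 6 | *L* = 8 | *L* = 10 |
|---|---|---|---|
| 8 weeks | 6/8 = 75% (4/8 = 50%) | 100% (6/8 = 75%) | 100% (8/8 = 100%) |
| 12 weeks | 6/12 = 50% (4/12 = 33%) | 8/12 = 67% (6/12 = 50%) | 10/12 = 83% (8/12 = 67%) |
| 24 weeks | 6/24 = 25% (4/24 = 17%) | 8/24 = 33% (6/24 = 25%) | 10/24 = 42% (8/24 = 33%) |

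One refinement: for a 10-week course starting in weeks 16-24, the window figure is 7/8 = 87.5%, because the next interval is already 12 weeks.

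**Longest gap.** Suppose the course starts just before a scheduled visit and the assessment is done as soon as it ends. The gap is then *I* + *L*: 8 + 6 = 14 to 8 + 10 = 18 weeks in the 8-week phase, 18-22 weeks in the 12-week phase, and 30-34 weeks in the 24-week phase. These are upper ends; a course starting earlier in the interval gives a shorter gap. If one visit is skipped outright, the gap is 16, 24 or 48 weeks.

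**Two consecutive assessments blocked.** This is what the Section 5.4.4 censoring rule needs. For courses starting in weeks 0-16, P = (*L* − 8)/8 on nominal dates and (*L* − 10)/8 with windows, bounded to 0-100%:

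- *L* = 6 or 8: 0%.
- *L* = 10: 2/8 = 25%, or 0% with windows.
- *L* = 12 (assumed): 4/8 = 50%, or 2/8 = 25%.
- *L* = 16 (assumed): 100%, or 6/8 = 75%.

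For courses of 6-10 weeks in the 12- and 24-week phases the result is 0%. No passage supports 12 or 16 weeks; those lines only show where the rule would begin to apply.

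**The case against.** Section 4.2 has a legitimate purpose: tumor shrinkage produced by steroids should not be credited to study drug. It can be read as governing the investigator's rating and not the CT, whose schedule stands in Section 4.1.22 without a steroid exception. The scan on suspected progression is mandatory there, against a softer instruction in Section 4.2. Section 4.1.23 adds examinations and hematology when no scan is taken, with suspected progression reported within 24 hours. Table 3-2 is expressly guidance. The 6-10 week course joins two passages, and the one on resolution does not mention steroids. ACP-319 has been stopped, and Appendix 5 now covers only Cycles >12, so the 8-week arithmetic concerns data already collected. The primary objective is safety, and the primary efficacy endpoint is the overall response rate. Finally, how a withheld assessment is classed is a detail that an analysis plan, not seen here, may settle.

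Much of this limits the size of the effect, but it does not remove the conflict. Section 4.2 speaks of performing assessments, and a site may reasonably withhold them.

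A reader might also infer four stronger things that the protocol does not support:

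- **Deaths are dated late.** A death counts on its own date unless two or more consecutive assessments were missing before it.
- **Events are routinely censored out.** On the 6-10 week figures this is reachable only near 10 weeks in the 8-week phase, and not at all with the windows.
- **A blocked end-of-Cycle-2 scan removes a subject from the Efficacy-evaluable population.** Any later evaluable assessment keeps the subject in, and that population serves only sensitivity analyses (Section 5.2).
- **Every subject with toxicity is affected.** Many toxicities are managed without steroids, and a short course can fall between scans.

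**Conclusion.** The point holds as a contradiction with a directional consequence. Section 4.2, read as written, conflicts with Section 4.1.22 and works against Section 4.5. Following it delays documented progression selectively in subjects with steroid-treated toxicity and so biases PFS and duration of response upward.

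A 6-10 week course blocks at least one assessment in 75-100% of cases in the 8-week phase (50-100% with windows), with gaps of up to about 14-18 weeks instead of 8. This rests on the assumed course length and a uniformly random start. The overall bias cannot be sized, because the protocol does not say how many subjects will receive such steroids. Loss of events through the censoring rule is a possibility for longer courses only.

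**What to change.** Reconcile Section 4.2 with Sections 4.1.22 and 4.5 by limiting it to the crediting of response. For example:

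*Scheduled tumor assessments, and those prompted by suspected progression, continue during systemic or enteric corticosteroids for a treatment-emergent condition. A new CR or PR seen on such an assessment is not credited until it is shown off steroids. Progression documented on such an assessment counts on its own date.*

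I would not also count absence of progression on steroids without qualification. Steroids may mask progression, and that would bias in the same upward direction.

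In Section 5.4.4, add a sensitivity analysis of PFS and duration of response. It should count as an event any progression or death that follows assessments withheld under Section 4.2, in place of censoring it. This also covers data already collected, which a change to Section 4.2 cannot recover.

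The cost is a short rewording of Section 4.2, one added sentence in Section 5.4.4 and a little extra analysis. No scans are added beyond those Section 4.1.22 already calls for, and no treatment rule changes. The remaining downside is that steroids may hide progression at some scans.
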